8.3.2 Cardiovascular Effects

Rapid heart rate, decreased heart rate, palpitations, increased blood pressure, decreased blood pressure, dizziness, fainting, cyanosis are listed as potential side effects of the components of XFBD.

Table 8.3.2 – Selected Cardiovascular Adverse Event Grading (CTCAE)

Grade	1	2	3	4	5
Chest pain – cardiac	Mild pain	Moderate pain; pain on exertion; limiting instrumental ADL; hemodynamically stable	Pain at rest; limiting self care ADL; cardiac catheterization; new onset cardiac chest pain; unstable angina		
Cyanosis		Present			
Dizziness	Mild unsteadiness or sensation of movement	Moderate unsteadiness or sensation of movement; limiting instrumental ADL	Severe unsteadiness or sensation of movement; limiting self care ADL		
Hypertension	Systolic BP 120 - 139 mm Hg or diastolic BP 80 – 89 mm Hg;	Systolic BP 140 – 159 mm Hg or diastolic BP 90-99 mm Hg if previously WNL; change in baseline medical intervention indicated; recurrent or persistent (≥ 24 hrs); symptomatic increase by	Systolic BP \geq 160 mm Hg or diastolic BP \geq 100 mm Hg; medical intervention indicated; more than one drug or more intensive therapy than previously used indicated;	Life threatening consequences (e.g., malignant hypertension, transient or permanent neurologic deficit, hypertensive crisis); urgent intervention indicated	Death

		>20 mm Hg (diastolic) or to >140/90 mm Hg; monotherapy indicated initiated			
Hypotension	Asymptomatic, intervention not indicated	Non-urgent medical intervention indicated	Medical intervention indicated; hospitalization indicated	Life-threatening consequences and urgent intervention indicated	Death
Palpitations	Mild symptoms; intervention not indicated	Intervention indicated			
Syncope				Fainting, orthostatic collapse	

In the event of grade 1 or greater cardiovascular symptoms, the study staff must refer the participant to their primary health care providers. For grade 2 or greater events participants must be referred to their health care provider for evaluation and study agent is discontinued.

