For example, ephedrine can be isolated and extracted from *ephedrae herba* (麻黃 *mahuang*). Ephedrine is a stimulant that excites the sympathetic nervous system, constricting blood vessels to act as a pressor and bronchodilator. In traditional Chinese medicine, the function of *ephedrae herba* is recognized similarly and is mostly used to treat bronchial asthma and prevent asthma attacks. (20-22)

Another example is *Glycyrrhizae radix et rhizoma* (甘草 *gancao*), also known as Chinese liquorice, which is a medicinal and can also be used as a sweetener in food products. The medicinal function includes clearing heat (including the reduction of fever), removing toxins (anti-infection, anti-infective), loosening and transforming phlegm to eliminate, suppressing cough, easing tension, and relieving pain. This medicinal is used in the treatment of sore throat, oral mucosa ulcers, cough, palpitations, and pain.

Generally, the design of a TCM prescription takes into account the source of the illness, the resulting symptoms, the external environment, and the personal constitution of the patient. In the following delineation, this document focuses on the aspects of a broad application TCM in which the prescription is balanced to be less dependent on environmental and individual factors for general application.

Potential Risks of XFBD

XFBD contains *ephedra herba*, which has levels of ephedrine and pseudoephedrine. Both are known sympathomimetic agents, which can cause an increase in blood pressure and heart rate. The level of ephedrine and pseudoephedrine in each packet is at most 15mg or 30mg per day. In some over-the-counter (OTC) medication, the daily dose of pseudoephedrine can exceed 300 mg, which is 10 times the daily dosage of ephedrine and pseudoephedrine in XFBD.

armeniaceae semen amarum with levels of amygdalin, or laetile. In TCM prescription theory and analysis, the levels of amygdalin are lower in the XFBD combination than in the plant *armeniaceae semen amarum* alone. The level of *armeniaceae semen amarum* in each packet is at most 80mg per day. Various studies have shown that 80mg is well below the level of toxicities manifesting.

Assessment of Potential Risks and Benefits

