3.3 Stratification

Randomization will be stratified by “high” versus “low” risk of severe disease, where “high” risk is defined by any of the following:

- Patients aged 60 years and older
- Patients having at least one of the following conditions under control:
 - Chronic lung disease including pulmonary fibrosis, COPD, pulmonary hypertension, moderate to severe asthma
 - Immunocompromised status due to disease (for example, those living with HIV with a CD4+ T-cell count of <200/mm³)
 - Immunocompromised status due to medication (for example, persons taking 5 mg or more of prednisone equivalents a day, cancer therapies)
 - Solid organ transplant, hematologic stem cell transplant, rheumatological disease or inflammatory bowel disease on immunosuppressants
 - Severe obesity (body mass index [BMI] >40; may be based on self-report of height and weight)
 - Hypertension requiring treatment by more than one agent.
 - Cardiovascular disease including coronary artery disease, congestive heart failure, valvular heart disease
 - Diabetes
 - Chronic kidney disease including stage 3-4 CKD.
 - Chronic liver disease including cirrhosis, autoimmune hepatitis, uncontrolled hepatitis.

4. SELECTION AND ENROLLMENT OF PARTICIPANTS**4.1 Recruitment****4.1.1 Recruitment**

This trial will recruit study participants through community health care sites and programs (Appendix 2 that lists the initial site) that are performing SARS-CoV-2 testing of symptomatic patients. The initial site is based in Los Angeles County.

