4.3.7 Known allergy/sensitivity or any hypersensitivity to components of XFBD

4.3.8 Active drug or alcohol use or dependence that, in the opinion of the site investigator, would interfere with adherence to study requirements.

4.3.9 Has known prior kidney disease.

4.3.10 Has known cirrhosis, acute liver disease or uncontrolled chronic liver disease.

4.3.11 Has known severe coronary artery disease.

4.3.12 Has known narrow angle glaucoma.

4.3.13 Has greater than two or a single uncontrolled underlying comorbid condition including cardiovascular disease (coronary artery disease, heart failure, valvular heart disease), hypertension, diabetes, chronic lung disease, chronic kidney disease, chronic liver disease, immunocompromised (HIV or daily users of more than 5 mg/day of prednisone), prior organ transplant.

4.3.14 Fulfils the FDA EUA criteria of at high risk for progressing to severe COVID-19. This includes high-risk individuals specified in the EUA who meet at least one of the following criteria: Body mass index (BMI) \geq 35; Chronic kidney disease; Diabetes mellitus; Immunocompromising condition/immunosuppressive disease; Currently receiving immunosuppressive treatment; Aged \geq 65 years; or Aged \geq 55 years and have: Cardiovascular disease, or Hypertension, or Chronic obstructive pulmonary disease/other chronic respiratory disease. If the patient is not able to receive the EUA agent because of unavailability this exclusion may be waived.

4.3.15 Women who are currently pregnant or breastfeeding.

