5.4.2 Potential Drug-Drug Interactions

Medicinal	Latin	Drug-Drug Interactions (DDI)	Special Consideration
麻黄	Ephedrae Herba	
Do Not Use Together:
 
 MAO Inhibitors - ephedrae herba's main component is ephedrine and MAO inhibitors may enhance the hypertensive effect of ephedrine. Ergot Derivatives - ephedrae herba's main component is ephedrine and ergot derivatives may enhance the hypertensive effect of ephedrine Inhalation Anesthetics - ephedrae herba's main component is ephedrine and inhalation anesthetics may sensitize the heart to arrhythmic actions of ephedrine. Digoxin^a – ephedrae herba's main component is ephedrine and digoxin may sensitize the heart to arrhythmic actions of ephedrine 
Potential DDIs:
 
 Calcium channel blocker Angiotensin II Antagonists Alpha-/Beta-blockers Alpha-/Beta-agonists Guanethidine (NE blocker) Methyldopa Clonidine Theophylline Phenobarbital 	Renal failure – ephedrine is mostly excreted renally
苦杏仁	Armeniacae Semen Amarum	Potential DDIs: 
 CNS depressants (benzodiazepines, barbiturates) 	
生石膏	Gypsum Fibrosum	Potential DDIs: 
 Tetracyclines Levodopa Digoxin 	
苍术	Atractylodis Rhizoma		Increases CYP3A4 activity (69)
广藿香	Pogostemonis Herba		
青蒿	Artemisiae Annuae Herba	
Do Not Use Together:
 
 Artemether – enhances toxic effect of Artemisinin Lumefantrine – enhances toxic effect of Lumefantrine 
Potential DDIs:
 
 Dapsone 	Increases CYP3A4 and 2B6 activity

马鞭草	Verbena Herba		
虎杖	Polygoni Cuspidati Rhizoma et Radix	Zidovudine – decreases clearance, increases toxicity (68)	Long term, large dosage can reduce synthesis of coagulation factors in the liver
芦根	Phragmitis Rhizoma		
葶苈子	Descurainiae Semen		
化橘红	Citri Grandis Exocarpium		Inhibits CYP3A4, 1A2 (70)
甘草	Glycyrrhizae Radix et Rhizoma	Potential DDIs: (68) 
 • Diuretics (other than potassium-sparing ones) • Digoxin • Aspirin • Reserpine • Glucocorticoid • Sulfonamides • Theophylline 	Medications metabolized by the liver – induces liver enzymes and can accelerate the metabolism of liver metabolized drugs Induces CYP3A4, 2B1, 1A2

^a This has been theorized due to the mechanism of action for ephedrae herba and digoxin. However, no clinical study has been conducted to confirm the interaction.

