Drugs that are listed above as “Do Not Use Together” are prohibited and patients receiving such agents are ineligible for study participation. Given the short duration of administration of the XFBD patients receiving drugs listed as “Potential DDIs” are eligible, but, in the event of adverse events, such a DDI will be considered by the medical monitor in consultation with the patients’ health care provider.

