6.2.4 Documentation from a health care/provider encounter - Remote

If the screening evaluation indicates either an encounter with a health care provider or symptoms greater than mild COVID-19 with shortness of breath (see table 3 above), documentation from the health care provider encounter will be obtained. This must include vital signs, SpO2 to permit classification of COVID-19 as mild or moderate which are eligible or greater than moderate which are not eligible for participation. The participants consent and HIPAA authorization will be required to obtain this health information from the provider.

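### No blood pressure reading is scheduled before or after dosing, so the grade 2 hypertension stop cannot act on a silent rise in a participant with no care encounter, and hypertension is probably under-counted.

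*Combined protocol and SAP*

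**What the plan says.** **The risk.** Section 2.1 (Potential Risks of XFBD) says of ephedrine and pseudoephedrine: "Both are known sympathomimetic agents, which can cause an increase in blood pressure and heart rate".

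**The rule.** Section 8.3.2 has two tiers. Referral starts at grade 1: "In the event of grade 1 or greater cardiovascular symptoms, the study staff must refer the participant to their primary health care providers". Stopping starts at grade 2: "For grade 2 or greater events participants must be referred to their health care provider for evaluation and study agent is discontinued". Table 8.3.2 places grade 2 hypertension at 140–159 systolic or 90–99 diastolic if earlier values were normal, alongside some criteria based on treatment or symptoms. Grade 3 starts at 160 systolic or 100 diastolic, with no condition on earlier values.

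**The measurements.** Table 6.1 has no vital-signs row. The kit in section 6.2.8 has no cuff. The visit descriptions in 6.2.9 to 6.2.16 take no reading. Section 6.2.4 asks for provider records at screening if there has been an encounter or symptoms are above mild: "This must include vital signs, SpO2 to permit classification of COVID-19 as mild or moderate". Blood pressure is not named. Section 6.2.7 lets mild cases combine screening and entry.

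**Who may be exposed.** Section 4.3.13 excludes uncontrolled comorbidity, and 4.3.14 excludes people at high risk under the EUA criteria, including hypertension from age 55. Of 4.3.14 the protocol adds: "If the patient is not able to receive the EUA agent because of unavailability this exclusion may be waived". Section 3.3 lists "Hypertension requiring treatment by more than one agent" as a high-risk stratification condition. Section 5.4.2 lists antihypertensive classes such as "Angiotensin II Antagonists" as potential interactions, and says that patients on drugs so listed "are eligible, but, in the event of adverse events, such a DDI will be considered by the medical monitor".

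**The concern.** A stopping rule expressed in mm Hg needs a pressure reading, and the plan schedules none. Raised pressure often causes no symptoms, so a system driven by symptoms and care encounters will miss some of the events that the rule is meant to catch. The first consequence is for participants: someone with a silent grade 2 rise and no encounter keeps taking the product.

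The second is for the data. Treatment-emergent safety is a primary outcome (10.2.1.3). Hypertension also feeds two secondary outcomes: adverse events leading to discontinuation (10.2.2.5), through the grade 2 stop, and grade 3–4 events (10.2.2.6). Section 10.6.2 compares both by treatment. The larger trial would plan its cardiovascular monitoring from a count in which few events cannot be separated from few measurements.

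**Working it through.** The plan gives no rate of hypertension or of its detection, so there is no figure to reproduce. The check has two parts.

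**1. How a reading can reach the study**

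| Route | Where | Who it covers |
|---|---|---|
| Scheduled study reading | Table 6.1; 6.2.8; 6.2.9–6.2.16 | Nobody |
| Provider vital signs before dosing | 6.2.4 | Those with an encounter or above-mild symptoms |
| Record review after dosing | 6.2.9–6.2.16; 8.3 | Those whose pressure was taken in care |
| Referral for cardiovascular symptoms | 8.3.2 | Those with symptoms |
| App or telephone report | 7.1 | Those who volunteer a value |

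A participant with a silent rise, no encounter and no volunteered home reading appears in no post-dose row.

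**2. What incomplete capture could do (illustration)**

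Inputs: n = 30 per arm (section 3). True risk r of grade 2 or higher hypertension and share c of true cases captured are both assumptions. False counts are set to zero.

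Recorded risk = r × c. Chance of recording no event = (1 − r × c)^30.

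| r | c = 100% | c = 50% | c = 20% |
|---|---|---|---|
| 5% | 0.95^30 = 21.5% | 0.975^30 = 46.8% | 0.99^30 = 74.0% |
| 10% | 0.90^30 = 4.2% | 0.95^30 = 21.5% | 0.98^30 = 54.5% |
| 20% | 0.80^30 = 0.1% | 0.90^30 = 4.2% | 0.96^30 = 29.4% |

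With everyone measured, 0/30 gives a one-sided 95% upper bound of 1 − 0.05^(1/30) = 9.5%. Dividing by c, the same 0/30 is compatible with a true risk of up to 9.5/0.5 = 19% at half capture, or 9.5/0.2 = 48% at one-fifth capture.

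**Between arms.** Take true risks of 20% and 5%, a ratio of 4. If capture is 15% on XFBD and 30% on placebo, the recorded risks are 3.0% and 1.5%, a ratio of 2. With the capture shares swapped they are 6.0% and 0.75%, a ratio of 8. Nothing in the documents says which is nearer the truth.

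**What the proposed change could recover.** Suppose a share o of participants own a cuff, owners are fully captured and others are captured at 20%, so c = o + 0.2 × (1 − o). At r = 10%, o = 30% gives c = 44% and (1 − 0.044)^30 = 25.9%; o = 50% gives c = 60% and (1 − 0.060)^30 = 15.6%. Without the change the figure is 54.5%. This is a best case, because three post-dose spot readings will not catch every rise. Among 9 or 15 owners per arm, zero events would still leave upper bounds of 1 − 0.05^(1/9) = 28% or 1 − 0.05^(1/15) = 18%.

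**The case against.** **The stop is not dead.** A reader might infer that it can never act. That goes too far: symptoms lead to mandatory referral, records of encounters are obtained, and electronic records are reviewed at the study contacts. The gap is confined to silent rises without an encounter.

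**False positives are limited.** One might also infer that a high count would merely reflect pre-existing hypertension. The documents do not support that. Grade 2 by reading requires earlier normal values. Section 7.1 requires worsening from baseline, with clinical significance decided by the medical monitor. A blinded randomised placebo arm balances pre-existing high readings in expectation. Some misclassification remains possible, mainly at grade 3, which has no condition on earlier values.

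**Other mitigations exist.** Section 5.4.1 bars other ephedrine and pseudoephedrine products, MAO inhibitors, ergot derivatives and digoxin. Section 4.3 excludes kidney disease and severe coronary disease. These reduce risk but measure nothing. No study reading backs the judgement that hypertension is controlled, 4.3.14 can be waived, and it does not exclude controlled hypertension below age 55.

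**Remote follow-up is a declared choice.** Section 8.3 says that adverse events are assessed remotely, and 10.6.1 limits the health-event models to planning. The plan nowhere claims that few hypertension events would show safety. This lowers the weight of the point, but the stop still lacks its input. Section 8.3.4 says openly that several measured events are captured only through encounter records; 8.3.2 has no such statement for hypertension.

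**Some material is not visible.** Appendix VI shows only three app screens, so an app question on blood pressure cannot be fully ruled out. No schedule row, kit item or visit description provides for one.

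**Conclusion.** The point holds in a limited form. If the plan is followed exactly, the grade 2 stop cannot act on an asymptomatic rise in a participant who has no care encounter and volunteers no reading. Hypertension is therefore probably under-ascertained in the primary safety outcome and the two secondary outcomes that it feeds.

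The structural gap rests on the text. Its size does not: the 4%, 21% and 55% chances of an empty count at 10% true risk depend on assumed risk and capture. A reader might conclude that the gap favours XFBD, but the documents do not show whether measurement would differ by arm, so the direction of any between-arm bias is unknown. This is a cheap improvement to a planning pilot, not a reason to reject its design.

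**What to change.** (a) At screening, ask whether the participant owns a home blood pressure cuff. For owners, add app fields for a pre-dose reading on Day 0/1 and for readings on Days 3, 7 and 14, all existing contacts. Apply the 8.3.2 grading and stop as written, with medical monitor review and no mandatory repeat reading before stopping.

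(b) In 10.6, report by arm the number with a pre-dose reading and the number with at least one post-dose reading, from home or electronic record, beside the hypertension count in all treated participants.

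(c) State in 10.6 that few or no hypertension events is not evidence against a pressor effect unless most participants were measured.

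**Cost.** One screening question, one app field at four time points, and a few counts and a sentence in 10.6; no new visits or equipment. The readings would come from a self-selected subset using unvalidated cuffs, silent rises in non-owners would stay unseen, and a few more participants may stop treatment. A cuff in every kit would close the gap more fully but needs extra resources.

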8.3.3 Nervous and Psychiatric Events

Headache, psychosis, insomnia, heatstroke, nervousness, anxiety, strokes, seizures, coma; are listed as potential side effects of the components of XFBD.

Table 8.3.3 – Selected Nervous System and Psychiatric Adverse Event Grading (CTCAE)

Grade	1	2	3	4	5
Anxiety	Mild symptoms; intervention not indicated	Moderate symptoms; limiting instrumental ADL	Severe symptoms; limiting self-care ADL; hospitalization indicated	Life-threatening consequences; urgent intervention indicated	
Depressed levels of consciousness	Decreased level of alertness	Sedation; slow response to stimuli; limiting instrumental ADL	Difficult to arouse	Life-threatening consequences; coma; urgent intervention indicated	
Headache	Mild pain	Moderate pain; limiting instrumental ADL	Severe pain; limiting self-care ADL		
Insomnia	Mild difficulty falling asleep, staying asleep or waking up early	Moderate difficulty falling asleep, staying asleep or waking up early	Severe difficulty falling asleep, staying asleep or waking up early		
Psychosis	Mild psychotic symptoms	Moderate psychotic symptoms (disorganized speech;	Severe psychotic symptoms (paranoid, extreme	Life-threatening consequences; threats of harm to self or others;	Death

		impaired reality testing)	disorganization) hospitalization not indicated; new onset	hospitalization indicated	
Stroke	Incidental radiographic findings only	Mild to moderate neurologic deficit; limiting instrumental ADL	Severe neurologic deficit; limiting care ADL; hospitalization	Life-threatening consequences; coma; urgent intervention indicated	Death
Seizure	Brief partial seizure and no loss of consciousness	Brief generalized seizure	New onset seizures (partial or generalized); multiple seizures despite medical intervention	Life-threatening consequences; prolonged repetitive seizures	Death

Grade 1 Anxiety and insomnia do not require treatment discontinuation. For grade 2 anxiety or insomnia the study agent is discontinued. For all other grade 1 or greater events in table 8.3.3 participants are instructed to discontinue study medication or placebo and must be referred to their health care provider for management.

8.3.4 Other side effects

Fatigue, excessive sweating, muscle weakness, weight gain, dehydration, liver damage, reduced testosterone levels, sudden death, blood in the urine, frequent urination, or low white blood cell count.

Table 8.3.4 – Selected Other Adverse Event Grading (CTCAE)

Grade	1	2	3	4	5
Fatigue	Fatigue relieved by rest	Fatigue not relieved by rest; limiting instrumental ADL	Fatigue not relieved by rest, limiting self-care ADL		
Urinary frequency	Present	Limiting instrumental ADL, medical management indicated			
Dehydration	Increased oral fluids indicated; dry mucous membranes; diminished skin turgor	IV fluids indicated	Hospitalization indicated	Life-threatening consequences; urgent intervention indicated	Death
Hypoglycemia	<LLN - 55 mg/dL; <LLN - 3.0 mmol/L	<55 – 40 mg/dL; <3.0 - 2.2 mmol/L	<40 - 30 mg/dL; <2.2 - 1.7 mmol/L	<30 mg/dL; <1.7 mmol/L; life threatening consequences;	Death

				seizures	
White blood cell decreased	<LLN - 3000/mm3; <LLN - 3.0 x 10e9 /L	<3000 - 2000/mm3; <3.0 - 2.0 x 10e9 /L	<2000 - 1000/mm3; <2.0 - 1.0 x 10e9 /L	<1000/mm3; <1.0 x 10e9 /L	
Testosterone deficiency	Asymptomatic; mild symptoms with no intervention indicated	Replacement therapy initiated			
Hepatic failure			Asterixis; mild encephalopathy; drug-induced liver injury (DILI); limiting self-care ADL	Life-threatening consequences; moderate to severe encephalopathy; coma	Death
Hematuria	Asymptomatic; clinical or diagnostic observations only; intervention not indicated	Symptomatic; urinary catheter or bladder irrigation indicated; limiting instrumental ADL	Gross hematuria; transfusion, IV medications, or hospitalization indicated; elective invasive intervention indicated; limiting self-care ADL	Life-threatening consequences; urgent invasive intervention indicated	Death

In the event of grade 1 or 2 fatigue the study agent may be continued, the study participant may contact their primary health care provider. The study agent should be discontinued, and the patient referred to their primary health care providers for grade 3 fatigue.

In the event of all other grade 1 or greater other side effects in table 8.3.4 the study staff must refer the participant to their primary health care providers and discontinue study agent.

Dehydration, hypoglycemia, white blood cell decreased, testosterone deficiency, hepatic failure (measure of hepatic damage) and hematuria are captured on review of medical records for participants who have a health care encounter.

